For adherence and viral suppression at endline, both of which will be dichotomized, we will conduct chisquare tests. We will also explore associations between treatment exposure and secondary outcomes using multiple linear regression models:

1. Social support

Model:	Multiple Linear Regression
Outcomes:	Change in social support score from baseline to endline (ss_avg_chng, individual sub- scales)
Exposures:	Study group (intervention v. comparison)
Covariates:	Age, sex, education at baseline, depression score at baseline, social isolation score at baseline

2. HIV knowledge/treatment literacy

Multiple Linear Regression Model:

Analysis Plan: Using Social Media to improve ART Retention and Treatment outcomes among youth living with HIV in Nigeria - The Youth SMART study

Outcomes: Change in knowledge score from baseline to endline (know chng)

Study group (intervention v. comparison) Exposures:

Covariates: Age, sex, education at baseline

3. Self-reported adherence

Model:	Multiple Logistic Regression
Outcomes:	Adherence at endline
Exposures:	Study group (intervention v. comparison)
Covariates:	Age, sex, education at baseline, household hunger score at baseline, time on ART at baseline, social support sub-scales, adherence at baseline

4. Viral load

Model:	Multiple Linear Regression
Outcomes:	Viral load at endline
Exposures:	Study group (intervention v. comparison)
Covariates:	Age, sex, education at baseline, household hunger score, adherence, time on ART at baseline, social support sub-scales

We will check that the following assumptions of multiple regression are met:

- Independence of observations (i.e. independence of residuals) ٠
- Linear relationships between dependent variable and each independent variable, and between dependent variable and the independent variables collectively. Method: Scatterplots
- Homoscedasticity variance does not change along line of best fit. Method: Plotting studentized • residuals against unstandardized predicted values
- No multicollinearity. Method: Inspect correlation coefficients and VIF values •
- No significant outliers, highly influential points, etc. Method: Exploratory data analysis
- Normal distribution of residuals. Method: Histogram with normal curve fitted, and normal p-plot of residuals

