Objective 4. To document the costs of the intervention and calculate the unit cost per YLHIV retained. Intervention costs will also be descriptively compared to the costs of adolescent-focused, in-person support groups in the region.						
Cost to put the intervention in place	Training costs (travel, per diem, venue rental, materials)	Study financial records	Descriptive: unit cost			
Implementation costs	Monthly facilitator meetings (transportation and refreshments)	SIDHAS and study financial records	Descriptive			
	Facilitator stipend					
	Equipment (phones) and supplies (airtime/data bundles)					
Estimated in-person	Facilitator stipend	SIDHAS financial	Descriptive			
support group costs	Venue costs	records				
	Transportation costs for facilitator and participants	In-person support group reports (no individual-level data)				
	Refreshments					
	Equipment/supplies for meetings					
Objective 5 : To document participant engagement and perspectives regarding the content and delivery of the intervention to inform scalability and sustainability.						
Engagement	Number of sessions in which participants actively post comments or reply to comments.	Grytics	Descriptive			
	Number of comments per session.					
Perspectives on content and delivery	Perspectives on topic relevancy, clarity, usefulness.	Structured questionnaires	Descriptive			
	Perspectives on content structure (components of sessions)	IDIs	Qualitative			
Perspectives on content and delivery	tent Perspectives on delivery frequency, facilitator engagement, medium of	Structured questionnaires	Descriptive			
	engagement.	IDIs	Qualitative			
Objective 6 : To document implementation and health care provider and support group facilitator perspectives regarding intervention content and delivery to inform scalability and sustainability.						
Fidelity of implementation	Ability to push out correct messages, hold regularly scheduled group chats as directed in intervention guide.	Grytics	Descriptive			

VII. Additional analyses

We will assess the construct validity of the MOS-SSS and HIV Stigma Scale-12 through confirmatory factor analysis. Both scales have been developed in high-income countries and have been found to have good psychometric properties in other settings.

Step 1. Correlation matrix

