For each scale, we will first present a polychoric correlation matrix between all variables included in the scale, looking for medium to high correlations between items (see below), and ideally with few items having correlations smaller than ± 0.1 . We will then use the matrix command to store the correlation matrix.

STATA commands:

polychoric [var names]
matrix r=r(R)

Step 2. Goodness-of-fit

MOS-SSS proposed factor structure:

- Tangible Support (latent construct=TAN)
 - o [q309] Someone to help you if you were confined to bed
 - o [q310] Someone to take you to the doctor if you needed it
 - o [q311] Someone to prepare your meals if you were unable to do it yourself
 - o [q312] Someone to help with daily chores if you were sick
- Emotional/Informational Support (latent construct=EMI)
 - o [q301] Someone you can count on to listen to you when you need to talk
 - o [q302] Someone to give you information to help you understand a situation
 - o [q303] Someone to give you good advice about a crisis (serious problem)
 - o [q304] Someone to confide in or talk to about yourself or your problems
 - o [q305] Someone whose advice you really want
 - o [q306] Someone to share your most private worries and fears with
 - o [q307] Someone to turn to for suggestions about how to deal with a personal problem
 - o [q308] Someone who understands your problems
- Affectionate Support Subscale (latent construct=AFF)
 - o [q313] Someone who shows you love and affection
 - o [q314] Someone to love and make you feel like you belong
 - o [q315] Someone who hugs you
- Positive Social Interaction Subscale (latent construct=POS)
 - o [q316] Someone to play with
 - o [q317] Someone to get together with for relaxation
 - o [q318] Someone to do something enjoyable with

HIV Stigma Scale-12 proposed factor structure:

- Personalized stigma (latent construct=PER)
 - \circ ~ [q214] Some people avoid touching me once they know I have HIV
 - o [q215] People I care about stopped calling after learning I have HIV
 - o [q216] I have lost friends by telling them I have HIV
- Disclosure concerns (latent construct=DIS)
 - o [q217] Telling someone I have HIV is risky

- o [q218] I work hard to keep my HIV a secret
- o [q219] I am very careful who I tell that I have HIV
- Concerns about public attitudes (latent construct=PUB)
 - o [q220] People with HIV are treated like outcasts
 - o [q221] Most people believe a person who has HIV is dirty

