 - o [q222] Most people are uncomfortable around someone with HIV
- Negative self-image (latent construct=NEG)
 - o [q223] I feel guilty because I have HIV
 - o [q224] People's attitudes about HIV make me feel worse about myself
 - o [q225] I feel I'm not as good a person as others because I have HIV

We will evaluate the goodness-of-fit of the proposed factor structures using CFI and/or RMSEA. We will report point estimates and confidence intervals and will accept the proposed factor structure if fit statistics are acceptable (CFI \ge 0.9, RMSEA \le .10 or upper bound of RMSEA CI \le .12)⁸.

STATA commands:

```
sem (proposed latent construct and factors here), from($r) stand
estat gof, stats(all)
estat mindices
```

If the fit statistics are not acceptable, we, we will evaluate the model's modification indices to determine whether the factor structure can be revised slightly (for example, adding a path between terms if there is a theoretical or conceptual reason to support doing so). If this approach does not produce a model with acceptable fit statistics, we will conduct an exploratory factor analysis to evaluate alternative factor structures. =Once arriving at a factor structure with acceptable fit statistics, we will assess convergent and discriminant validity by assessing whether the scales are correlated to items that should hold similarities (i.e. social isolation, depression) and not correlated to items that should not (i.e. HIV knowledge). We will assess this descriptively through scatter plots and test these

Secondarily, we will assess the relationship between the scale and the primary outcome. We hypothesize the following:

- MOS-SSS
 - o Positive relationship between change in MOS-SSS score and retention
- HIV Stigma Scale-12
 - Negative relationship between change in HIV Stigma Scale-12 (higher scores indicate higher stigma) and retention

If any of the variables specified above have ≥5% missingness (missing or refused), a multiple imputation model will be run as a secondary analysis. The imputation model will include additional variables that are theoretically related to the variables being imputed (Chantala & Suchindra; Stuart, 2009; White, 2011): Age, sex, education at baseline, depression, social isolation, HIV knowledge/treatment literacy.

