Although there is some controversy as to whether to round categorical variables after imputation (Allison, 2005), we will round the values in each variable in order to facilitate interpretation of results and given expected very small proportion of missing data.

The multiple imputation procedure involves 3 phases (Rubin, 1996; Yuan, 2000):

Analysis Plan: Using Social Media to improve ART Retention and Treatment outcomes among youth living with HIV in Nigeria - The Youth SMART study

PHSC #1151489; Version 1.0; December 2019

⁸ RMSEA is a measure of the average of the residual variance and covariance; good models have RMSEA values that are at or less than 0.08. CFI is an index that fall between 0 and 1, with values greater than 0.90 considered to be indicators of good fitting models (Hu et al., 1999.). For the purposes of this analysis we will use slightly less stringent cutoffs.

- 1. The missing data are filled in m times to generate m complete data sets.
- 2. The m complete data sets are analyzed by using standard procedures.
- 3. The results from the m complete data sets are combined for inference.

The miset of commands (mi set, mi impute, and mi estimate) will be used for the multiple imputation procedure. To allow results to be reproducible, a random-number seed will be set. M=10 imputed datasets will be created.

VIII. Qualitative analysis

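### The fit rule for the MOS-SSS and stigma scale is met in about 98–100% of samples even when a scale has only one dimension, so passing it cannot show that the subscales are distinct

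*SAP*

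**What the plan says.** SAP section VII sets the aim: "We will assess the construct validity of the MOS-SSS and HIV Stigma Scale-12 through confirmatory factor analysis". Step 1 builds a polychoric correlation matrix, "looking for medium to high correlations between items". Step 2 lists a four-factor structure for each scale: 18 MOS-SSS items split 4, 8, 3 and 3, and 12 stigma items split 3, 3, 3 and 3.

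On the decision, Step 2 says: "We will evaluate the goodness-of-fit of the proposed factor structures using CFI and/or RMSEA". The team "will accept the proposed factor structure if fit statistics are acceptable", that is, when CFI is at least 0.9 and RMSEA is at most 0.10, or its upper confidence bound is at most 0.12. A footnote explains: "For the purposes of this analysis we will use slightly less stringent cutoffs". Modification indices, and then exploratory factor analysis, follow only if fit is not acceptable. The later convergent and discriminant step relates each scale to social isolation, depression and HIV knowledge.

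The result is used elsewhere. SAP section IV.C (Social Support) lets the factor analysis inform which score is presented and used, and the stigma entry says the same. In section VI, Objective 2, model 1 has as outcomes "Change in social support score from baseline to endline (ss_avg_chng, individual sub- scales", and models 3 and 4 take the MOS-SSS subscales as covariates.

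**The concern.** The aim is to show that the subscales hold up in this setting. The rule asks only whether a four-factor model reproduces the observed correlations. It does not ask whether four factors are needed. If respondents answer all items in one undifferentiated way, the four-factor model still fits and the rule returns a pass.

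Two uses would then rest on an untested distinction:

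- **Scoring of social support.** The score ss_avg averages four subscale means and item 19. That weighting makes sense if the subscales are distinct. If they are not, the plain total, also defined in section IV.C, is the natural score, and the rule cannot signal this.
- **Model 1.** Separate results for tangible, emotional/informational, affectionate and interaction support could be read as effects on different constructs.

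For the stigma scale, only the construct-validity statement and the reported subscale scores are at stake.

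**Working it through.** **Inputs from the documents.** The thresholds and item groupings are those above. The sample is 250 per arm, so n = 500 (SAP section III). The SAP gives no error rate for the rule, so there is no stated figure to reproduce.

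**Assumptions.** Loadings, factor correlations and response distributions are not in the documents. The ranges used were loadings 0.4 to 0.8; five categories for MOS-SSS items and four for stigma items where ordinal; symmetric or skewed responses; n = 200, 350 and 500. Acceptance required CFI and RMSEA together. Reading the SAP's "and/or" as either one alone would accept at least as often.

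**Step 1: nesting.** With p items there are p(p+1)/2 variances and covariances. The four-factor model has p loadings, p residual variances and 6 factor correlations.

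| Scale | Moments | Four-factor df | One-factor df | Difference |
|---|---|---|---|---|
| MOS-SSS, p = 18 | 171 | 171 − 42 = 129 | 171 − 36 = 135 | 6 |
| Stigma, p = 12 | 78 | 78 − 30 = 48 | 78 − 24 = 54 | 6 |

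The 6 df are the factor correlations. Setting all of them to 1 gives the one-factor model. For one-dimensional data the four-factor model is therefore correctly specified, and with continuous items its chi-square has expectation close to its df.

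**Step 2: how far the RMSEA limit lies.** RMSEA = √[(χ² − df)/(df × (n − 1))]. To exceed 0.10 at n = 500, χ² must be above df + 0.01 × df × 499.

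- MOS-SSS: 129 + 643.7 = 772.7, against an expected 129 with SD √258 = 16.1. That is about 40 SDs away.
- Stigma: 48 + 239.5 = 287.5, against an expected 48 with SD √96 = 9.8. That is about 24 SDs away.

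For such data only the CFI limit could ever bind.

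**Step 3: simulated acceptance when the scale is one-dimensional.**

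| Setting | Four-factor model accepted |
|---|---|
| n = 500, continuous, loadings 0.4–0.8 | 3000 of 3000 (mean CFI 0.991–0.999; largest RMSEA 0.046) |
| n = 500, ordinal, polychoric, loadings 0.5–0.7 | 98–100% |
| n = 500, ordinal, Pearson, loadings 0.5–0.7 | 100% |
| n = 350, continuous | 100% |
| n = 200, continuous | 96.5–100% |
| n = 500, loading 0.4, strongly skewed, polychoric with unadjusted ML | 49.5% (MOS-SSS), 57% (stigma) |

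In the last row the one-factor model, which is true there, passes in only 44.5% and 43%. The misfit comes from the estimator and says nothing about dimensionality.

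**Step 4: are the cut-offs the cause?** Tightening to CFI ≥ 0.95 and RMSEA ≤ 0.06 still accepts 98–100% at n = 500 with continuous items. The cause is the missing rival model.

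**Step 5: what a comparison adds** (n = 500, continuous; loadings 0.7 where factors are distinct). The four-factor model passes the SAP rule in 100% of samples at true factor correlations of 0.5, 0.7, 0.85, 0.9 and 0.95, just as it does at 1. A 6-df chi-square difference test prefers four factors in 3–7% of one-dimensional samples, in 100% at correlations 0.5 to 0.9, and in 99% (MOS-SSS) or 72.5% (stigma) at 0.95. With unadjusted ML on polychoric correlations the false-preference rate rises to 15–47%, so the test must be scaled for ordinal data.

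**Step 6: weights in ss_avg.** Item 19 has weight 1/5 = 20%. Each of the eight emotional/informational items has 1/5 × 1/8 = 2.5%. In the plain total every item has 1/19 = 5.3%.

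**The case against.** The case on the other side has force on scope.

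- **The rule is not empty.** When two dimensions cut across the subscales, it accepts 0–12% of samples at a correlation of 0.3 to 0.7 between them, though 100% at 0.85. A reader might infer that construct validity is never tested. That goes too far: the item correlation matrix and the external checks also count.
- **The problem would probably be visible.** The planned command prints standardized output. In one-dimensional samples at least one estimated factor correlation reaches 1 or more about 86–98% of the time. What is missing is a written decision on what to do then.
- **Joint covariates.** It is tempting to say that overlapping subscales spoil models 3 and 4. Objective 2 already plans a multicollinearity check with VIF, and overlap among adjustment covariates does not by itself distort the study-group coefficient.
- **Stigma.** One might infer that stigma subscales feed the outcome models. None of the four Objective 2 regression models uses them, and section IV.C plans change scores only for the stigma total.
- **Acceptance as a gate.** Model 1 lists the subscales whatever the factor analysis shows; the SAP says only that the result informs scoring. These models are introduced as exploratory, and the mediation analysis names a total score.
- **When a one-factor model fails.** It would be wrong to say this happens only at factor correlations near 0.5. At 0.7 it already passes the SAP thresholds in only 4.5% (MOS-SSS) and 8% (stigma) of samples.

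These points narrow the consequence. None of them lets the rule tell one dimension from four.

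**Conclusion.** The point holds in limited form. Passing the section VII rule is not evidence that the subscales are distinct, because one-dimensional data pass in about 98–100% of samples at n = 500 with loadings of 0.5 to 0.7. That figure rests on assumed loadings and response distributions. The exception, weak and strongly skewed items, lies outside the inter-item correlations the SAP hopes to see. The nesting argument does not depend on those assumptions.

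The practical effect is secondary. It concerns the choice between ss_avg and the plain total, the reading of the subscale outcomes in model 1, and, for stigma, the validity statement and reported subscale scores. A reader might fear for the retention result; the primary analysis uses neither scale.

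**What to change.** In SAP section VII, Step 2:

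1. Fit a one-factor model for each scale alongside the four-factor model, and report the factor correlations.
2. Treat the four-factor structure as supported only if it meets the existing thresholds and also improves on the one-factor model by a pre-stated comparison suited to ordinal data, for example a scaled chi-square difference or a CFI difference. The margin is for the team to choose and write down in advance.
3. If it is not supported, use the total as the main social-support score and label the MOS-SSS subscale results in model 1 as not shown to be distinct constructs. They need not be dropped.

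A fixed ceiling on factor correlations is not needed. A ceiling of 0.85, for instance, would discard subscales at a true correlation of 0.9, where the comparison still detects four factors in 100% of samples (continuous items).

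This is a cheap improvement. It costs one extra model per scale and a few sentences in the SAP; the downside is possibly less emphasis on subscale results.
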